7.2.2. Primary Analysis of the Primary Endpoint

If systemic allergic reactions are observed, we will compare the proportions of participants experiencing a systemic allergic reaction to the Pfizer-BioNTech COVID-19 Vaccine and independently to the Moderna COVID-19 Vaccine between the HA/MCD and comparison populations. The point estimate of the difference in proportions between populations within each vaccine is estimated as p_1-p_0 with $p_1=x_1/n_1$ and $p_0=x_0/n_0$ and will be reported, together with the corresponding 95% exact unconditional confidence interval. The proportion difference will be tested using a Barnard's Exact Unconditional Test with a two-sided test using the central method of doubling the one-sided p-value. No multiplicity adjustment will be applied to these two primary endpoints.

```
*** Primary Analysis (Barnard's);
ods output BarnardsTest=BarnardsTestOutput;
proc freq data = d_1 order = data;
  title "Primary";
  where dose = 'E' and protocol<5;
  tables group*resp / riskdiff;
  exact riskdiff barnard;
* High computational power, only run on an as needed basis;
run;
```

The p-value is equal to (BARNARDSTESTOUTPUT.NVALUE1)*2 where BARNARDSTESTOUTPUT.NAME1='XPL_RDIF1'.

```

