##### 14.4.2. Primary Analysis of Primary Endpoints

The primary analyses will estimate the proportion of participants who experience a systemic allergic reaction (CoFAR Grade 2 and above regardless of tryptase, or CoFAR Grade 1 with elevated tryptase [ $1.2 \times$  baseline plus 2 ng/ml]) within the 90-minute post-vaccination observation period to either dose of the Pfizer-BioNTech COVID-19 Vaccine and independently the Moderna COVID-19 Vaccine for both the HA/MCD and comparison populations. These four proportions will be accompanied by their 95% exact confidence intervals.

If systemic allergic reactions are observed, we will compare the proportions of participants experiencing a systemic allergic reaction to the Pfizer-BioNTech COVID-19 Vaccine and independently to the Moderna COVID-

19 Vaccine between the HA/MCD and comparison populations. The point estimate of the differences in proportions between populations within vaccines will be reported, together with their corresponding 95% exact unconditional confidence intervals. Exact p-values will be calculated using an unconditional test, as some cell counts are likely to have an expected value less than 5. No multiplicity adjustment will be applied for these two primary endpoints. Details of the implementation of the exact unconditional confidence intervals and p-value calculations will be included in the statistical analysis plan.

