#### 14.7. Sample Size Considerations

The within vaccine sample size of 1700 participants, 1020 in the HA/MCD population and 680 in the comparison population was determined to detect a minimum proportion difference between the two populations of approximately 0.01 with at least 80% power, assuming a two-sided unconditional exact test. The proportion is assumed to be 0.0001 (1/10,000) in the comparison group and 0.01 (1/100) in the HA/MCD group (see [Table 14.7](#)). Power was calculated using an unconditional exact test, with the significance level of the test targeted at 0.05.

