**Table 14.7. Expected Rates, Number of Systemic Allergic Reactions, and Sample Size**

Rate (Number) Sample Size	Pfizer-BioNTech COVID-19 Vaccine	Moderna COVID-19 Vaccine	Total (Sample)
Comparison (40%)	0.0001 (0) 680	0.0001 (0) 680	1360
HA/MCD (60%)	0.01 (10) 1020	0.01 (10) 1020	2040
Total	0.006 (10) 1700	0.006 (10) 1700	0.006 (20) 3400

Under the scenario described in [Table 14.7](#), the proportion difference within a vaccine between the two populations is estimated at 0.01 with an unconditional exact 95% confidence interval (0.003, 0.018) and unconditional exact test p-value < 0.05. This illustration shows the expected precision of the estimated proportion difference under the assumed scenario.

This sample size also allows the following precision for estimation of risk in the HA/MCD group within each vaccine sample. If no reactions are observed out of 1020, the corresponding exact 95% confidence interval is (0, 0.0036), which rules out a risk as high as 1/275. If instead, the observed proportion is 10/1020 (i.e., about 0.01), then the 95% confidence interval is (0.005, 0.018).

For children, the within vaccine sample size of 300 participants was chosen. Under this scenario, we expect 180 in the HA/MCD population and 120 in the comparison population. This will detect a minimum proportion difference between

the two populations of approximately 0.05 with approximately 80% power, assuming a two-sided unconditional exact test. The proportion is assumed to be 0.0001 (1/10,000) in the comparison group and 0.05 (1/20) in the HA/MCD group.

Furthermore, a sample size goal of 300 children into the Pfizer-BioNTech COVID-19 vaccine allows for the following precision for the estimation of risk in the HA/MCD group. If no reactions are observed out of the 180 HA/MCD participants, the corresponding exact 95% confidence interval is (0, 0.020), which rules out a risk as high as 1/50. If instead the observed proportion is 2/180 (i.e., about 0.01), then the 95% confidence interval is (0.001, 0.039).

The sample size calculations do not account for dropouts since we expect that number to be extremely low. Although vaccine is widely available, there are difficulties getting into the registration systems and few individuals who receive an initial dose do not return for the second dose.

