# R: Primary Analysis (Barnard's) p-value
library(exact2x2)
t <- with(d_1 %>% filter(dose == 'E' and protocol<5),
table(group,resp))
uncondExact2x2(t[1,2],sum(t[1,]),
t[2,2],sum(t[2,]),
alternative = "less",
parmtype = "difference",
method   = "score",
midp     = TRUE,
control  = ucControl(nPgrid=5000),
conf.int = FALSE)
```

Exact unconditional confidence limits for the risk difference are obtained with SAS procedure PROC FREQ and the RISKDIFF option in the EXACT statement. These RISKDIFF options request exact unconditional 95% confidence limits for the risk (proportion) and risk difference for the 2x2 table respectively. PROC FREQ computes the confidence limits by the tail method, which inverts two separate one-sided exact tests of the risk difference, where the tests are based on the score statistic (Chan and Zhang 1999). The size of each one-sided exact test is at most $\alpha/2$, and the confidence coefficient is at least $(1-\alpha/2)$.

If there is an issue with the calculation of the Barnard's Exact Unconditional Test, we will perform the Risk difference estimates, asymptotic 95% confidence intervals, and p-values using SAS procedure PROC FREQ and the RISKDIFF option without an EXACT statement.

```
*** Primary Analysis (Asymptotic);
proc freq data = d_1 order = data;
  title "Primary";
  where dose = 'E' and protocol<5;
  tables group*resp / riskdiff;
run;
```

Additionally, we will compare the proportion of participants experiencing a systemic allergic reaction (as defined in section 7.2.1) between HA/MCD adult (18 years and older at enrollment) and HA/MCD child (less than 18 years of age at enrollment) populations for each vaccine separately. Children who qualified for the study on the basis of uncontrolled allergic asthma will be excluded from this analysis. The point estimate of the difference in proportions between adult and child populations within each vaccine will be estimated along with its corresponding 95% exact unconditional confidence interval. The proportion difference will be tested using a Barnard's Exact Unconditional Test with a two-sided test using the central method of doubling the one-sided p-value. No multiplicity adjustment will be applied.

In the event that there are not enough subjects in a particular population, the reaction rate will be described descriptively.

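### The doubled Barnard p-value in SAP 7.2.2 is valid but takes its maximum near a 99.6% reaction probability; a prespecified Berger-Boos form would raise primary power from 85.4% to 92.4%

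*SAP*

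**What the plan says.** Protocol 14.4.2 commits to an exact unconditional analysis: "Exact p-values will be calculated using an unconditional test, as some cell counts are likely to have an expected value less than 5". SAP 7.2.2 names Barnard's test and makes it two-sided by doubling ("two-sided test using the central method of doubling the one-sided p-value"). The SAS statement is "exact riskdiff barnard". The R call uses the score statistic, mid-p and "ucControl(nPgrid=5000". Neither call limits the range of the common reaction probability, and neither document mentions such a limit. Both code blocks keep only participants from protocol versions before 5.

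Protocol 14.7 sizes each vaccine comparison at "1020 in the HA/MCD population and 680 in the comparison population", "with the significance level of the test targeted at 0.05", for at least 80% power. On rates: "The proportion is assumed to be 0.0001 (1/10,000) in the comparison group and 0.01 (1/100) in the HA/MCD group". For children, the same section expects 180 v 120 participants at 0.05 v 0.0001, to detect a difference between "the two populations of approximately 0.05 with approximately 80% power".

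**The concern.** An unconditional test removes the unknown common reaction probability by taking the worst case over its range. Here the planned risks are 0.01% to 1%, but the worst case occurs where almost everyone reacts. The p-value is then set by a situation that the data rule out.

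The plan expects about 10 v 0 reactions per vaccine, so one event on the rejection boundary affects power noticeably. Comparing the populations is one of the trial's two principal aims. The power statement also allows nothing for dropout, although SAP 7.2.1 removes participants who had no dose 1 reaction and lack dose 2 data.

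**Working it through.** **Inputs.** n1 = 1020 and n0 = 680, risks 0.01 and 0.0001, two-sided 0.05 (protocol 14.7); doubled one-sided Barnard p (SAP 7.2.2).

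**Method.** Order all tables by the pooled score z. The one-sided p is the largest probability, over the common reaction probability, of a table at least as extreme as the one observed. Double it. Power is the sum over x0 of P(X0 = x0) × P(X1 ≥ c(x0)), where c(x0) is the smallest significant HA/MCD count. Terms beyond x0 = 2 are negligible.

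**1. The plan's own power.** c = 7, 11, 14 for x0 = 0, 1, 2.
- Power = 0.9343 × 0.8832 + 0.0635 × 0.4421 + 0.0022 × 0.1495 = 0.854, which meets at least 80%.
- Child sizes (c = 7, 10, 13): 0.9881 × 0.8002 + 0.0119 × 0.4126 + a negligible term = 0.796, consistent with approximately 80%.

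**2. Where the maximum falls for 6 v 0.**
- Pooled rate 6/1700 = 0.00353; z = (6/1020) / √[0.00353 × 0.99647 × (1/1020 + 1/680)] = 2.004.
- The largest one-sided tail is 0.0282, at a common probability of 0.996; doubled p = 0.056.
- The 60:40 split explains this. If nearly everyone reacts, 0 non-reactors of 1020 against 3 of 680 already gives z = 2.12, beyond 2.004. At the low end it takes six reactions in the larger group.
- Over common rates below 5%, the doubled value is 0.042.
- The R mid-p version also gives 0.056, because 6 v 0 has almost no probability at 0.996 and half-weighting it changes nothing.

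**3. Berger-Boos, gamma = 0.0001.**
- The 99.99% exact interval for 6/1700 is 0.0004 to 0.0130.
- The largest tail inside it is 0.0196; p = 2 × (0.0196 + 0.0001) = 0.039.

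| HA/MCD v comparison | Planned p | Berger-Boos p |
|---|---|---|
| 5 v 0 | 0.089 | 0.062 |
| 6 v 0 | 0.056 | 0.039 |
| 7 v 0 | 0.038 | 0.027 |

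**4. Power after the change.** c = 6, 9, 12.
- 0.9343 × 0.9410 + 0.0635 × 0.6904 + 0.0022 × 0.3257 = 0.924, a gain of 7.0 points.
- With gamma = 0.001, c = 6, 10, 12 and power is 0.916, a gain of 6.2 points.

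**5. Error rate at 1020 v 680.**
- At common rates up to 2%, the planned test's one-sided rejection rate is at most 0.0144 of the 0.025 allowed.
- The Berger-Boos test reaches at most 0.0247 there, and 0.0231 at common rates of 98.5% to 99.98%.

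**6. Other uses of Barnard's test.** Assume 2040 HA/MCD participants split 2:2:1:1, which gives 680, 680, 340 and 340.
- SAP 7.3.4 pools both placebo arms, so it compares 680 v 680. 4 v 0 is significant under both tests (0.0477 and 0.0469) and 3 v 0 under neither (0.0969 and 0.0971). Nothing is gained.
- SAP 7.3.3 (priming) compares 680 with 340. With reactions only in the 340 group, Berger-Boos just adds 0.0002. With reactions only in the 680 group, the same calculation moves 7 v 0 from 0.084 to 0.048.

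**The case against.** The strongest objection is that nothing in the plan is wrong. The protocol promises an exact unconditional test, the SAP delivers a valid one, and both power statements hold on recomputation. That stands.

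Four further points also stand in whole or part.
- **Cause.** The maximum near 99.6% does not act alone. An unrestricted Barnard test ordered by |z|, without doubling, gives p = 0.046 for 6 v 0. The doubling is nonetheless defensible, because it matches the tail-method interval in SAP 7.2.2, which inverts two one-sided tests. Berger-Boos keeps that structure.
- **Children.** A reader might infer that a planned child test gains 9 points. At 180 v 120 power does rise from 79.6% to 88.6%, but SAP 7.2.2 codes no such test. Its primary analysis stops at version 4.0, and its child comparison sets HA/MCD adults against HA/MCD children. The figure bears only on the power statement in protocol 14.7.
- **Reach.** A reader might also extend the change to every Barnard test in the SAP. The 7.3.4 boundary does not move, and 7.3.3 gains in one direction only.
- **Timing.** HA/MCD status is an enrolment group and is not masked. Participants under versions 1.0 to 4.0 were unblinded individually, and the DSMB sees outcome data about every 500 completers. Lowering the boundary from 7 to 6 events at this stage has a credibility cost.

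The practical effect is also narrow: the planning scenario of 10 v 0 is significant under both tests (about 0.012 and 0.007), and the Clopper-Pearson intervals for each group do not change.

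**Conclusion.** The point holds as a cheap improvement to the primary HA/MCD v comparison test. At 1020 v 680 and 0.01 v 0.0001, the smallest significant result with no comparison reactions moves from 7 v 0 to 6 v 0. Power rises from 85.4% to 92.4%, and the chance of missing the target effect falls from 14.6% to 7.6%. The level is kept: adding gamma makes the p-value valid by construction, and the computed one-sided sizes are under 0.025.

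The documents do not support reading this as an invalid test or a missed power target.

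The gain rests on the 60:40 split, on the planned risks and on gamma. It persists if numbers fall short. At assumed sizes that are not in the documents, power goes from 82.0% to 90.3% at 969 v 646, and from 79.1% to 88.3% at 930 v 620.

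**What to change.** In SAP 7.2.2, for the primary HA/MCD v comparison test only:
- Specify the Berger-Boos form with gamma = 0.0001: maximise each one-sided p over the 99.99% exact interval for the common proportion, add gamma, then double.
- Invert the same test for the confidence interval of the difference. Otherwise p < 0.05 could appear beside an interval that includes 0.
- Report plain Barnard as a check.
- Restate the power in protocol 14.7, and label the child figure as a power statement with no matching test in SAP 7.2.2.
- Leave 7.3.4 as it is. A change in 7.3.3 is optional.

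The interim rule needs no change: the smallest attainable two-sided p is 2 × 0.0001 = 0.0002, below the 0.001 boundary.

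The cost is SAP wording and a short validated program for the p-value and interval, beyond the PROC FREQ code now specified. No more participants are needed. Gamma must be fixed in advance. The change and its date should be recorded in SAP section 11 before the study team sees any primary comparison result.

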# R: Primary Analysis (Barnard's) p-value
library(exact2x2)
t <- with(d_1 %>% filter(dose == 'E' and protocol<5),
table(group,resp))
uncondExact2x2(t[1,2],sum(t[1,]),
t[2,2],sum(t[2,]),
alternative = "less",
parmtype = "difference",
method   = "score",
midp     = TRUE,
control  = ucControl(nPgrid=5000),
conf.int = FALSE)
```

Exact unconditional confidence limits for the risk difference are obtained with SAS procedure PROC FREQ and the RISKDIFF option in the EXACT statement. These RISKDIFF options request exact unconditional 95% confidence limits for the risk (proportion) and risk difference for the 2x2 table respectively. PROC FREQ computes the confidence limits by the tail method, which inverts two separate one-sided exact tests of the risk difference, where the tests are based on the score statistic (Chan and Zhang 1999). The size of each one-sided exact test is at most $\alpha/2$, and the confidence coefficient is at least $(1-\alpha/2)$.

If there is an issue with the calculation of the Barnard's Exact Unconditional Test, we will perform the Risk difference estimates, asymptotic 95% confidence intervals, and p-values using SAS procedure PROC FREQ and the RISKDIFF option without an EXACT statement.

```
*** Primary Analysis (Asymptotic);
proc freq data = d_1 order = data;
  title "Primary";
  where dose = 'E' and protocol<5;
  tables group*resp / riskdiff;
run;
```

Additionally, we will compare the proportion of participants experiencing a systemic allergic reaction (as defined in section 7.2.1) between HA/MCD adult (18 years and older at enrollment) and HA/MCD child (less than 18 years of age at enrollment) populations for each vaccine separately. Children who qualified for the study on the basis of uncontrolled allergic asthma will be excluded from this analysis. The point estimate of the difference in proportions between adult and child populations within each vaccine will be estimated along with its corresponding 95% exact unconditional confidence interval. The proportion difference will be tested using a Barnard's Exact Unconditional Test with a two-sided test using the central method of doubling the one-sided p-value. No multiplicity adjustment will be applied.

In the event that there are not enough subjects in a particular population, the reaction rate will be described descriptively.

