#### 14.6. Statistical Hypotheses

All primary and secondary objectives will be based on two-sided superiority tests. For instance, the null and alternative hypotheses for the primary objectives are:

- $H_0$ : The proportion of participants with systemic allergic reactions in the comparison population is equal to the proportion of participants with systemic allergic reactions in the HA/MCD population
- $H_A$ : The proportion of participants with systemic allergic reactions in the comparison population is different from the proportion of participants with systemic allergic reactions in the HA/MCD population

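### The R code printed for the primary p-value in SAP 7.2.2 omits the doubling that the text requires; repaired and with HA/MCD as the first row, it returns about half the stated p-value

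*SAP*

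**What the plan says.** SAP 7.2.2 compares HA/MCD with comparison participants within each vaccine by Barnard's exact unconditional test, as a "two-sided test using the central method of doubling the one-sided p-value". The SAS listing is followed by a rule for reading its output: "The p-value is equal to (BARNARDSTESTOUTPUT.NVALUE1)*2".

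The next listing, headed "R: Primary Analysis (Barnard's) p-value", calls `uncondExact2x2` with the score method, `alternative` set to `less` and `midp` set to `TRUE`. No multiplication by 2 appears in the call or in any sentence about it. Neither the prose nor the SAS code mentions mid-p for this test. The filter joins its two conditions with the word `and`. Row 1 of the table is whichever level of `group` comes first, and the SAP does not show that order.

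Protocol 14.6 states: "All primary and secondary objectives will be based on two-sided superiority tests". Protocol 14.7 calculates power for a two-sided unconditional exact test, "with the significance level of the test targeted at 0.05".

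**The concern.** The SAP prints two listings for one primary p-value, and they do not return the same quantity. For SAS, the text supplies the step from one-sided to two-sided. For R, under a heading that presents the output as the primary p-value, that step is missing. An analyst who repaired the filter and compared the R output with 0.05 would be running a one-sided 5% test in place of the two-sided test in the protocol.

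The expected counts are small (Table 14.7 expects about 10 reactions against 0 per vaccine), so a factor of two in p can decide significance. The SAS listing carries a comment that its exact run is computationally heavy, which makes it more likely that the R route is used in practice.

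The same method serves the adult-child comparison in 7.2.2 and secondary endpoints 1, 2 and 6, whose analysis sections refer back to 7.2.2.

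**Working it through.** **Inputs.** Per vaccine n1 = 1020 HA/MCD and n0 = 680 comparison; rates 0.01 and 0.0001; two-sided level 0.05 (Protocol 14.7). Doubling rule and R settings from SAP 7.2.2. Assumed: HA/MCD is row 1 and the filter is repaired. The p-values were computed from the definition of the test; exact2x2 and SAS were not run.

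**Formulas.** With p̄ = (x1 + x0)/(n1 + n0), tables are ordered by z = (x1/n1 − x0/n0) / √[p̄(1 − p̄)(1/n1 + 1/n0)].
- One-sided exact p = maximum over the common rate π of the probability of all tables with z at least as large as observed.
- Mid-p is the same, less half the probability of tables with z equal to the observed value.
- Stated rule: 2 × one-sided exact p. R block: one-sided mid-p, undoubled.

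Example, 5 v 0: p̄ = 5/1700 = 0.00294, difference = 5/1020 = 0.00490, standard error = 0.00268, z = 1.83.

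**Step 1: the plan's own power.** Under the doubled rule, power at 1020 v 680 is 0.854, or 0.862 if the borderline table 10 v 1 (doubled p = 0.0507) is counted as significant. Both agree with the stated 80% or more. For children (180 v 120, 0.05 v 0.0001) the doubled rule gives 0.796, matching the stated figure of approximately 80%; the undoubled rule would give 0.946. The planning figures therefore fit the doubled test.

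**Step 2: p-values at 1020 v 680.**

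| HA/MCD v comparison | One-sided exact | R block (one-sided mid-p) | Stated rule (doubled) |
|---|---|---|---|
| 5 v 0 | 0.0444 | 0.0444 | 0.0889 |
| 6 v 0 | 0.0282 | 0.0282 | 0.0564 |
| 7 v 0 | 0.0190 | 0.0190 | 0.0380 |
| 8 v 1 | 0.0444 | 0.0444 | 0.0889 |
| 9 v 1 | 0.0318 | 0.0296 | 0.0636 |

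5 v 0, 6 v 0, 8 v 1 and 9 v 1 are significant at 0.05 only in R; 7 v 0 is significant in both. The same split appears at 180 v 120 (5 v 0: 0.041 against 0.084; 6 v 0: 0.027 against 0.055).

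**Step 3: source of the gap.** Mid-p changes the 5 v 0 and 6 v 0 values by less than 0.0001, because the maximum lies at a common rate near 1, where the observed table has almost no probability. At 9 v 1 mid-p does contribute, and the ratio is 0.0636/0.0296 = 2.15. The rest is the missing factor of 2.

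**Step 4: chance of disagreement at 0.05.** At the design rates, power judged at 0.05 is 0.962 under the R rule. The difference from the stated rule is 0.962 − 0.862 = 0.100, or 0.962 − 0.854 = 0.108, depending on 10 v 1: about 10 to 11%. With an HA/MCD rate of 0.5% or 0.6% (an assumption, not in the documents) and the comparison rate at 0.0001, it is about 31%.

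**Step 5: the block as printed.** R rejects `and` as a syntax error (checked in R 4.3.3), so as printed the block returns nothing. R's default alphabetical order puts Comparison before HA/MCD. If `less` then tests the opposite direction, p is about 1 at 5 v 0 and 6 v 0.

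**The case against.** The strongest reply is that the p-value is already defined. The prose requires doubling, the only p-value formula in 7.2.2 doubles, and the protocol is two-sided. The SAS listing does not double inside the code either; a sentence after it does, and the R block merely lacks its own sentence. The SAP also reports an exact unconditional confidence interval that inverts two one-sided score tests of size at most α/2 each. An undoubled 0.044 or 0.028 would be expected to stand beside an interval that includes 0, which should alert a careful reader.

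This stands as to intent. A reader might infer that the SAP sets up two rival primary tests, or that the primary test is really one-sided at 5%; the documents support neither. The interval is a cross-check and not a correction: the R output would still carry the heading of the primary p-value.

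A reader might also infer that the SAS rule gives values above 1 when the difference has the other sign. That depends on which tail SAS writes to XPL_RDIF1. The documents do not say and SAS was not run, so it is something to check and not a finding.

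Nor can it be said without condition that R returns half the SAS value. The block needs repair before it returns anything, and with the other row order it would be significant at neither 5 v 0 nor 6 v 0.

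**Conclusion.** The R block does not compute the p-value that SAP 7.2.2 defines. It omits the doubling, adds an undocumented mid-p setting, does not parse, and leaves the direction of the test to an unstated factor order. With the filter repaired and HA/MCD as row 1, its output is about half the stated p-value, and results such as 5 v 0, 6 v 0, 8 v 1 and 9 v 1 would change from not significant to significant at 0.05. The chance of such a result is about 10 to 11% at the design rates and about 31% at an assumed HA/MCD rate of 0.5 to 0.6%. These figures assume the planned group sizes.

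The correction should be made because it concerns the primary p-value and could reverse a decision. It does not put the stated test or the sample size in doubt. Mid-p is a minor part of the discrepancy.

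**What to change.** Make the R block follow the governing text:
- replace `and` with `&` in the filter;
- set the order of `group` explicitly and state which population is row 1;
- set `midp = FALSE`;
- compute both one-sided exact p-values and report p = min(1, 2 × the smaller).

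Add one sentence saying that the same rule applies to the SAS output, and check which tail XPL_RDIF1 holds when the difference has the other sign. State that the adult-child comparison and secondary endpoints 1, 2 and 6 follow the corrected rule. Run both programs on a few small tables, such as 5 v 0, 6 v 0 and 9 v 1, and confirm that they agree.

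The cost is a few lines of SAP code and a short test run. The hypothesis, sample size and stated test do not change.

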    ((dose = 'P1' & Placebo = 'Yes') |
    (dose = 'D1' & Placebo = 'No' ));
  tables dose*resp / riskdiff;
  exact riskdiff barnard;
run;
```

Supportive Statistical Analyses

If there is an issue with the calculation of the Barnard's Exact Unconditional Test, we will perform a univariate logistic regression. NLMeans macro will be used to obtain the proportion difference and 95% confidence interval. There will be no adjustment for covariates

```
*** 1st dose comparison to Placebo (Sensitivity);
proc genmod data = d_1;
  title "1st dose comparison to Placebo (Sensitivity)";
  where group = 'HA/MCD' &
    ((dose = 'P1' & Placebo = 'Yes') |
    (dose = 'D1' & Placebo = 'No' ));
  class id dose;
  model resp(event = '1') = dose / dist=binomial link = logit;
  lsmeans dose / e ilink diff exp;
  store out=genmod;
  ods output coef = coeffs;
run;
%NLMeans(instore=genmod, coef=coeffs, link=logit, title= 1st dose
comparison to Placebo Prop Diff);
```

Handling of Missing Data

Participants with missing data for their placebo or 1st active dose will be removed from this analysis (complete case analysis).

Notes

The same analysis will be repeated for the Moderna COVID-19 Vaccine.

7.3.5. Secondary Endpoint 6

Endpoint: The proportion of participants who experience a systemic allergic reaction (CoFAR Grade 2 and above) within 48 hours of either dose of each vaccine.

Computation: A Grade 2 or higher systemic allergic reaction, categorized as yes or no, is defined as a participant having a Grade 2 or higher (per CoFAR Grading Scale V3.0) systemic allergic reaction within 48 hours to either active dose 1 or active dose 2 (categorized as yes) or to either active dose within 48 hours (categorized as no). Due to the nature of patient reported events, any systemic allergic reaction reported within 2 days after the date of injection will be counted as occurring within 48 hours.

Participants who do not have a systemic allergic reaction to the 1st active dose but missing data for their 2nd active dose will be removed from this analysis (complete case analysis).

Analysis: This analysis will be carried out as outlined in Section 7.2.2. A sensitivity analysis will be carried out as outlined in Section 7.2.3.

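### If Barnard's test cannot be computed, SAP 7.2.2 substitutes asymptotic output that, read as unpooled Wald, is significant from 4 v 0 reactions; the planned exact test needs 7 v 0

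*SAP*

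**What the plan says.** Protocol 14.4.2 gives its reason for exact inference: "Exact p-values will be calculated using an unconditional test, as some cell counts are likely to have an expected value less than 5". Protocol Table 14.7 expects about 10 reactions in HA/MCD and none in the comparison group for each vaccine.

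SAP 7.2.2 implements this as Barnard's test, with the one-sided p-value doubled, and an exact unconditional interval for the risk difference that inverts the score statistic. A comment in the SAS code reads "High computational power, only run on an as needed basis". R code for the Barnard p-value follows.

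The section then provides for a problem with the Barnard calculation, without saying what counts as one. In that case "we will perform the Risk difference estimates, asymptotic 95% confidence intervals, and p-values using SAS procedure PROC FREQ", using the RISKDIFF option and no EXACT statement. The printed fallback code requests no score, Newcombe or continuity-corrected method. Nothing requires the R code to be tried first.

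The interim test (SAP 10.1) and secondary endpoints 1, 2 and 6 (SAP 7.3.1, 7.3.2, 7.3.5) are all analysed by 7.2.2, so they inherit the fallback.

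**The concern.** The fallback gives up exactness in the very setting for which the protocol requires it. With no reactions in the comparison group, the unpooled variance takes nothing from that group: its estimated risk is treated as known to be zero, however few people it contains. The interval is then too narrow and the p-value too small.

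At stake is the second principal aim, whether HA/MCD risk is higher. With 4 to 6 reactions against none, the declared result would depend on whether a program finished running rather than on the data.

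**Working it through.** **Inputs**
- Group sizes (Protocol 14.7): "The within vaccine sample size of 1700 participants, 1020 in the HA/MCD population and 680 in the comparison population".
- Rates (Protocol 14.7): "The proportion is assumed to be 0.0001 (1/10,000) in the comparison group and 0.01 (1/100) in the HA/MCD group".
- Level (Protocol 14.7): "with the significance level of the test targeted at 0.05", two-sided.
- Test rule (SAP 7.2.2): doubled one-sided Barnard p.
- Assumption: asymptotic means the unpooled Wald interval and its matching z test.

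**1. The plan's own figures.** All 2x2 tables were ordered by the pooled score statistic, the one-sided tail was maximised over the common rate, and the result was doubled. The test then rejects at 7 or more v 0, 11 or more v 1, and 14 or more v 2. Power is the sum over x0 of P(X0 = x0) × P(X1 ≥ k(x0)), where k(x0) is that threshold. It comes to 85.4%, consistent with the stated "with at least 80% power, assuming a two-sided unconditional exact test". The Clopper-Pearson upper limit for 0/1020 is 0.0036, as the protocol says. For 10 v 0 the exact interval is (0.002, 0.018) against the protocol's (0.003, 0.018), a small difference that does not affect this point.

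**2. Wald at 4 v 0.** The difference is d = 4/1020 = 0.00392. Its standard error is √(0.00392 × 0.99608/1020 + 0) = 0.00196. So z = 2.004, p = 0.045, and the 95% CI is (0.0001, 0.0078). In general, with x v 0, z = √[x/(1 − x/1020)], which is close to √x. It passes 1.96 at x = 4 whatever the size of the comparison group. At 3 v 0, p = 0.083.

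**3. Pooled z at 4 v 0.** The pooled rate is 4/1700 = 0.00235. The standard error is √[0.00235 × 0.99765 × (1/1020 + 1/680)] = 0.00240. So z = 1.63 and p = 0.102.

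**4. Side by side at 1020 v 680**

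| Reactions | Wald p | Pooled z p | Doubled Barnard p |
|---|---|---|---|
| 4 v 0 | 0.045 | 0.102 | 0.136 |
| 5 v 0 | 0.025 | 0.067 | 0.089 |
| 6 v 0 | 0.014 | 0.045 | 0.056 |
| 7 v 0 | 0.008 | 0.030 | 0.038 |

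At 4 v 0 the exact unconditional interval is about (−0.002, 0.010). Its lower limit is −0.0002 at 6 v 0 and +0.0007 at 7 v 0.

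**5. Operating characteristics, summed over the binomial sample space**
- Wald 95% coverage is 93.3% at 1% v 0.01% and 87.8% at 0.5% v 0.01%. The score (Miettinen-Nurminen) interval covers 96.1% and 97.7%.
- Maximum two-sided Wald size, over common rates up to 3%, is 6.3%, near a common rate of 0.34%. The upper tail reaches 5.1% against a nominal 2.5%. The pooled score test has maximum size 5.0%.
- At the design rates Wald rejects with probability 97.8%, the exact test 85.4%.

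**6. Other sizes.** Both thresholds, 4 v 0 and 7 v 0, also hold at 600/400, 510/340, 450/300 and 180/120. They are particular to roughly 3:2 groups: the doubled exact test needs 4 v 0 at 500/500 and 10 v 0 at 600/300.

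**7. Interim.** Half the adult plan per vaccine is 510 v 340. At alpha 0.001, Wald rejects at 11 v 0 (p = 0.0008) and the exact test at 17 v 0 (p = 0.0009).

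**The case against.** **The fallback may never be used.** The code comment reports a heavy computation, not a failing one, and the SAP already prints a second exact route in R. A reader might infer that the switch is likely; the documents support no probability for it. This stands, so every figure above is conditional on the trigger.

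**The method is not named.** If a pooled z test was meant, the fallback first rejects at 6 v 0, one event before the exact test. A continuity-corrected Wald interval would match it at 7 v 0. This also stands, though the printed code asks for neither.

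**Part of the gap is conservatism of the exact test.** At 6 v 0 the Barnard tail is maximised at a common reaction rate of about 99.6%. Limiting the search to rates of 50% or less gives 0.045, which is significant. The argument does not rescue 4 v 0 or 5 v 0, where the same restriction gives 0.103 and 0.068 against Wald's 0.045 and 0.025.

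**Disagreement is not error.** Wald is significant and the exact test is not with probability 12.4% at 1% v 0.01%, and 47.3% at 0.5% v 0.01%. A reader might take these as false-positive rates. They are not: a true difference exists in both cases. The error measures are size and coverage.

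**The logistic fallback.** In SAP 7.3.3 and 7.3.4 the fallback is that "we will perform a univariate logistic regression", and a reader might object that this has no finite estimate when one group has no reactions. As a general criticism that fails. The priming analysis in 7.3.3 is skipped when either or both groups have no reactions, and the analysis in 7.3.4 is skipped when placebo has none. Most zero-cell cases never reach the model.

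**Limited reach.** The first principal aim, the separate proportions with Clopper-Pearson intervals, is untouched. At the planned 10 v 0, Wald and exact agree on significance.

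**Conclusion.** The point holds as a conditional weakness in SAP 7.2.2. If the fallback is triggered and is unpooled Wald, the significance threshold at 3:2 group sizes falls from 7 v 0 to 4 v 0. Coverage drops to between 87.8% and 93.3% in the two cases examined, and maximum two-sided size rises to 6.3%. The size inflation is modest; the under-coverage and the one-sided tail (5.1% against 2.5%) are the clearer faults.

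The result rests on three assumptions: the Wald reading, the planned allocation of about 3:2, and the SAP's doubling rule. The mid-p setting in the SAP's R code does not move the 7 v 0 threshold. The documents do not support calling the fallback probable, or attributing the whole 4-to-7 gap to Wald.

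**What to change.** In SAP 7.2.2:
1. State what counts as a failed Barnard calculation.
2. Require the R exact p-value to be tried before any asymptotic method, doubled as for SAS. As printed, that code switches off the confidence interval and uses the word *and* in its filter, which R does not accept, so it needs a small correction. Keep the exact interval if it can still be computed.
3. If the exact route also fails, use the score (Miettinen-Nurminen) interval and score test in place of plain RISKDIFF output. This is the statistic the exact interval already inverts.

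The interim test and secondary endpoints 1, 2 and 6 follow by reference. No general change to the logistic fallback in 7.3.3 and 7.3.4 is needed on this ground.

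The cost is a sentence or two and a code option. Fallback intervals become somewhat wider. The score test is not identical to the exact test: it still rejects at 6 v 0 (p = 0.045), one event earlier, but it holds its size at 5.0%.
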